Although there is still debate within the international community on the cost-effectiveness of screening pregnant women for chlamydia, United States clinical guidelines recommend that pregnant women below the age of twenty-five, pregnant women twenty-five years/older but with behavioral risk factors should undergo chlamydia screening[11]. According to an Australian study, when the prevalence of Chlamydia in pregnant women is greater than 11%, the potential benefit from screening will be higher than the cost of screening itself.[12] A review published in 2002 further suggests that when the prevalence of women is between 3.1-10%, screening of chlamydia can be cost-effective[13]. Previous studies have found that the prevalence of chlamydia in pregnant women in China was between 4.9% -14.0%[5 14], indicating a serious Chlamydia epidemic. In 2015, the reported incidence of genital Chlamydia in China was 37.18 / 100,000. Guangdong province reported an incidence of 150.88 / 100,000, second highest among all provinces, autonomous regions, and municipalities throughout China. Additionally, the number of newly reported cases are increasing. In 2016, there were 65,988 newly reported cases. Concurrently, compared with other nations, the incidence of spontaneous abortion, premature

birth and low birth weight children in China is also high. In 2015, the incidence of spontaneous abortion in China was about 5-15%; preterm birth was 6.1% [15]; and low birth weight was 6.3%[15]. In 2015 alone, there were 122,300 reported stillbirths in China, the fourth highest in the world[16], indicating a need for significant improvement in perinatal and neonatal health. Additionally, in January 2016, China completely liberalized its second child policy, welcoming a small fertility peak in 2017. In 2017, Guangzhou also saw increased childbirth with permanent resident births (including census registered and non-native residents living in Guangzhou more than 6 months) reaching 126,000. These increased births may also increase the burden of maternal, fetal, and newborn diseases in China.

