Despite the substantial burden of chlamydia and adverse pregnancy outcomes, no previous research has been conducted to examine the effects of genital chlamydia infection on adverse pregnancy outcomes in China. There is no clinical guideline on screening for genital Chlamydia infections in pregnant women. Therefore, it is important to understand the impact of genital Chlamydia in China through randomized controlled studies that explore the relationships between Chlamydial infection and adverse pregnancy outcomes, and the feasibility and effectiveness of screening and treatment. The purpose of this study is to 1.) clarify the causal relationship between genital *C. trachomatis* infection and adverse pregnancy outcomes and 2.) determine whether screening and treatment of genital *C. trachomatis* in pregnant women can reduce adverse pregnancy outcomes. The research team will screen pregnant women in Guangzhou for genital *C. trachomatis* to understand its prevalence. We will also conduct a randomized controlled trial to explore whether clinical treatment of *C. trachomatis*-positive patients can reduce adverse pregnancy outcomes, and neonatal chlamydial conjunctivitis and pneumonia. This study will have great scientific and social significance. Firstly, it will provide

an important reference for the formulation of public health policies, clinicians' treatment of chlamydia infection in pregnant women, and prevention of chlamydial infection in newborns. Secondly, it will be a valuable resource for the prevention of adverse pregnancy outcomes and neonatal infection associated with sexually transmitted diseases in other developing countries.

II. Purpose

1. To examine whether screening and treatment of genital C. trachomatis in pregnant women can reduce adverse pregnancy outcomes
2. To explore the effectiveness of screening and treatment of genital C. trachomatis in reducing mother-to-child transmission
3. To evaluate the cost-effectiveness of screening and treating chlamydial infections in pregnant women, and provide a basis for health policy decisions on how best to screen / treat

III. Hypotheses

1. Effective screening and treatment of pregnant women with genital C. trachomatis will reduce adverse pregnancy outcomes
2. Effective screening and treatment of pregnant women with genital C. trachomatis will reduce neonatal chlamydial conjunctivitis and pneumonia
3. C. trachomatis screening and treatment of pregnant women is cost-effective.

IV. Content

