Target population and sampling

This study will recruit pregnant women from a maternal/child health hospital in Guangzhou city and county. Guangzhou Women and Children Medical Center and Zengcheng Maternal and

Child Health Hospital (now Zengcheng Hospital of Guangzhou Women and Children Medical Center) are two key hospitals for perinatal health and pregnant women. In 2016, Guangzhou Women and Children Medical Center delivered 22,455 infants, the highest delivery volume among the hospitals throughout the city. Additionally, Zengcheng Hospital of Guangzhou Women and Children Medical Center provides prenatal care, delivery care, and other main medical services for pregnant women in Zengcheng district. Given the rich clinical research resources and experience of both hospitals, we have elected to conduct our large-scale randomized controlled clinical trial at these two hospitals.

Inclusion criteria: 1) pregnant women on their first visit to the hospital (regardless of gestational age); 2) aged 18 or above; 3) agree to participate and sign an informed consent. Exclusion criteria: 1) systemic or topical vaginal antibiotics were used within 2 weeks prior to the first perinatal visit; 2) diagnosed adverse pregnancy outcomes at recruitment (e.g., stillbirth); 3) pregnant women who refuse to participate in this study.

Sample size estimation

The sample size calculation was based on the following assumptions: 1, the conservative estimate of prevalence of Chlamydia is around 6% among pregnant women in Guangzhou; 2, our meta-analysis showed that the odd ratio of adverse pregnancy outcomes in infected pregnant women versus non-infected pregnant women was 1.8; 3), assuming a 5% significance level on both sides, with a 80% efficacy test and a 2% loss- to-follow-up rate, in order to demonstrate a significantly lower incidence of adverse pregnancy outcomes in the intervention group than in the control group (estimated at 10%, from preliminary data, unpublished results), the sample size

should be approximately 7,725 for each group with an overall target sample size of 15,450 (when $\beta = 0.8$, the estimated sample size is 15,449).

Alpha	OR	p^2	Power	# of positive samples	Prevalence (%)			Total sample size (include 2% loss-to-follow-up)		
					5	6	8	20,306	16,922	12,691
0.05	1.8	0. 1	0.9	995						
0.05	1.8	0. 1	0.8	757	5	6	8	15449	12874	9656

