* The prevalence of abortion, stillbirth, premature birth, low birth weight, SGA and neonatal deaths was 10.1% in the same cohort recruited by Guangzhou Women's Center for 2012-2017.

Questionnaire and follow-up

We will obtain informed consent from participants. We will inform them of the main purpose of the study and the research process (Annex 1). We will emphasize that participation is completely voluntary. Refusal or withdrawal will not affect medical treatment and health care services at the Center. All information obtained by the research group will be strictly confidential and shall not be shared with any other third parties prior to obtaining consent from the participants. After enrolment, we will conduct a baseline survey with all participants, collect relevant medical history, information, and urine samples. The survey will be carried out by the research staff at the Center. The survey content will be built on the questionnaire that is developed by the birth cohort at the Center. We will obtain information on socio-demographic characteristics, chronic medical history, other acute conditions during the first trimester of pregnancy(diagnosis and treatment), number of pregnancies, prior history of previous caesarean section, history of recurrent miscarriage, prior

history of ectopic pregnancy, history of psychiatric illness (e.g., depression), smoking/drinking habits, and history of second-hand smoke exposure. We will add other questions to collect information about history of sexually transmitted diseases and gynecological diseases (such as cervical surgery), whether or not systemic or topical antibiotics were used within the past one month, drug use, sexual behaviors, sexual partner history both before and during pregnancy, history of falls during pregnancy, previous experience of domestic violence, etc. (Annex 2).

Participant recruitment and randomization

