Our primary outcome is the occurrence of adverse pregnancy-related outcomes between the two groups, which include: 1) stillbirth (the definition of stillbirth in this study will use International Classification of Diseases (ICD-11): death prior to complete expulsion (pregnant ≥ 28 weeks) and death during extraction [17]); 2) Spontaneous abortion (less than 1000gms or less than 28 weeks); 3) Preterm labor (birth fewer than 37 weeks gestational age; Infants born before 28 weeks are considered very early-preterm; 28-32 weeks early-preterm; 32-37 weeks late-preterm. 4) Premature rupture of membranes (prior to onset of labor); 5) Low birth weight (2,499g or less); 6) Small for gestational age (weight below the 10th percentile); and 7) perinatal death.

Secondary Outcomes

The secondary outcomes include: C. trachomatis infection of the newborn, Chlamydial conjunctivitis, and pneumonia in the newborn. Laboratory methods for the diagnosis of neonatal

chlamydial infection include: 1) Detection of *C. trachomatis* by sampling from conjunctival scraps and nasopharyngeal/ pharyngeal posterior through direct fluorescence (DFA); 2) PCR and 3) chlamydia culture.

Common Chlamydia conjunctivitis clinical symptoms and supplementary examinations include eyelid and nasal congestion, or 2) catarrhal or mucopurulent secretions, occurring within 5-14 days after birth. It is possible for exudate adhesions to form pseudomembranes. If treatment is delayed more than two weeks, conjunctival follicles may also form.

Chlamydia pneumonia infection may appear insidiously. However, symptoms will usually appear in 4-12 weeks. Common clinical manifestations include nasal mucus secretion, nasal congestion, intermittent cough, shortness of breath, rales on auscultation. There is usually no fever or change in consciousness. Laboratory examinations may show normal white count but elevated eosinophils; moderate hypoxemia on arterial blood gas; bilateral interstitial markings on chest radiography.

Clinical Data Collection

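### The stated 80% power belongs to about 757 chlamydia-positive women; if all randomised women are compared, power is about 10–19%

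*Combined protocol and SAP*

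**What the plan says.** The Primary Outcome section of the combined protocol and SAP reads "Our primary outcome is the occurrence of adverse pregnancy-related outcomes between the two groups". It does not restrict this to infected women. The sample-size text says the number was chosen "in order to demonstrate a significantly lower incidence of adverse pregnancy outcomes in the intervention group than in the control group". Under Participant recruitment and randomization, women are allocated in blocks of 20, and testing of the intervention group follows allocation.

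The sample-size table works on another unit. It has a column for the number "of positive samples", with 757 at 80% power and 995 at 90%. The effect is an odds ratio of 1.8 for infected against non-infected women, with a reference risk of 10%. The adopted size is 7,725 per group, 15,450 in total.

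The stated aims point both ways. The introduction, just before II. Purpose, says the team will "conduct a randomized controlled trial to explore whether clinical treatment of *C. trachomatis*-positive patients can reduce adverse pregnancy outcomes". Purpose 1 is "To examine whether screening and treatment of genital C. trachomatis in pregnant women can reduce adverse pregnancy outcomes".

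**The concern.** The power statement and the comparison it is attached to appear to concern different women. An odds ratio of 1.8 is an effect among the infected. Randomisation is of everyone, so in a comparison of whole arms that effect is averaged over a large majority who are uninfected and cannot benefit from treatment for chlamydia. If the primary analysis includes all randomised women, the 80% does not describe it. The trial is meant to inform screening policy, so a null result carrying a stated 80% power could be taken to show that screening does not work when the design had little chance of showing that it does.

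**Working it through.** **Inputs from the plan (Sample size estimation):** two-sided 5% level; 80% power; 2% loss; odds ratio 1.8; reference risk 10%; prevalence 5%, 6% or 8%; total 15,450, allocated 1:1.

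**1. Reproduce the plan's totals.** Total = positives / prevalence / 0.98.

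| Positives | 5% | 6% | 8% |
|---|---|---|---|
| 757 (80% power) | 15,449 | 12,874 | 9,656 |
| 995 (90% power) | 20,306 | 16,922 | 12,691 |

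All six match the table, so the 80% is a statement about 757 infected women over both arms. The adopted 15,450 is the 5% entry, although the text assumes 6%.

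**2. Contrast among the infected.** Odds at 10% = 0.10 / 0.90 = 0.1111; × 1.8 = 0.2000; risk = 0.2000 / 1.2000 = 16.7%. The contrast is 16.7% against 10%, or 6.7 points.

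**3. Contrast between whole arms.** Control risk = prevalence × 16.7% + (1 − prevalence) × 10%. Intervention risk = 10%, if treatment removes all the excess and no control is treated before the outcome. Any effect of treating gonorrhoea is ignored, because no prevalence is given. Evaluable per arm = 15,450 × 0.98 / 2 = 7,570.

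**4. Power.** Pooled two-proportion z test; power = Φ(d/SE − 1.96) + Φ(−d/SE − 1.96).

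| Prevalence | Control vs intervention | d (points) | SE (points) | d/SE | Power | n per arm for 80% |
|---|---|---|---|---|---|---|
| 5% | 10.33% vs 10.00% | 0.33 | 0.491 | 0.68 | 10.4% | 129,030 |
| 6% | 10.40% vs 10.00% | 0.40 | 0.492 | 0.81 | 12.8% | 89,865 |
| 8% | 10.53% vs 10.00% | 0.53 | 0.493 | 1.08 | 19.1% | 50,841 |

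The 95% confidence interval half-width is 1.96 × √(2 × 0.1 × 0.9 / 7,570) = 0.96 points. That is 1.8 times the largest expected difference (0.96 / 0.53) and 2.9 times the smallest (0.96 / 0.33).

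**5. Other inputs, whole arms.** The introduction says "the prevalence of chlamydia in pregnant women in China was between 4.9% -14.0" per cent, so 14% is the top of the plan's own range. The reference risk comes from the table footnote, "The prevalence of abortion, stillbirth, premature birth, low birth weight, SGA and neonatal deaths was 10.1" per cent. That list omits premature rupture of membranes, which the primary composite includes, so the true base risk may be higher. The 15% and 20% below are assumptions.

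| Base risk | Power at 5% | 6% | 8% | 14% |
|---|---|---|---|---|
| 10% | 10% | 13% | 19% | 47% |
| 15% | 12% | 15% | 24% | 58% |
| 20% | 13% | 17% | 27% | 65% |

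- Taking 10% as the overall control-arm risk gives 10%, 13% and 19% at 5%, 6% and 8%.
- Taking 10% as the risk in infected controls gives 9%, 10% and 14%.
- If 90% of the excess is removed and 10% of infected controls are treated early (both assumed), power is 9%, 10% and 14%.

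**6. The infected set, equal arms, same test.** 757 positives give 77% at a 10% base risk, 89% at 15% and 94% at 20%. At 6% prevalence the trial yields 15,450 × 0.98 × 0.06 = 908 positives, with 84%, 93% and 97%. With the stated inputs, 80% power needs 814 positives in total (pooled test), or about 873 with continuity correction, so 757 does not follow exactly from the plan's own figures.

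**The case against.** The strongest reply is that infected women were always the intended set. The table counts positives, the introduction speaks of treating positive patients, and every control is tested after delivery or an adverse outcome, which a whole-arm comparison would not need. Positives can also be compared between the two groups, so the group wording is not decisive. At the text's own 6% prevalence the adopted total gives 84% power on that reading. The 757 may reflect a base risk nearer 12%: with continuity correction, 12% gives 754 and 992, close to the tabulated 757 and 995. Figure 1 and some removed pages could not be read and might identify the set.

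Much of this stands. The low power is conditional on the whole-arm reading, and the 77% at 757 is a minor point. But the plan never says the primary comparison is limited to positives, and Purpose 1 is about screening pregnant women. Post-delivery testing of controls also has a care rationale, given under Justifications of the control strategy.

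The infected-set reading brings its own difficulty. Two sections place control urine collection after delivery or an adverse outcome, while Questionnaire and follow-up says "we will conduct a baseline survey with all participants, collect relevant medical history, information, and urine samples". If the later timing governs, positivity is fixed at enrolment in one arm and after the outcome in the other, and the two subsets are not comparable by randomisation.

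**Conclusion.** The concern holds. The 80% is a calculation for about 757 infected women, attached to wording that compares the randomised groups, and the analysis set is not named in the available text. If all randomised women are compared, power is about 10–19% at 5–8% prevalence. This assumes a 10% base risk, an odds ratio of 1.8, all excess risk removed, no control-arm treatment before the outcome, and 2% loss. The last two effect assumptions are favourable to the trial. None of the variants examined reaches 80%; the most generous, 14% prevalence with an assumed 20% base risk, gives 65%. The statement of power must be corrected. The derivation of 757 and the timing of control urine are secondary, and the conclusion does not depend on them.

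**What to change.** 1. **Name the set the 80% refers to.** If the primary comparison is all randomised women, replace 80% with about 10–19% over 5–8% prevalence and list the assumptions. State that the result will be read from its confidence interval and that a null will not be taken as evidence against screening. This is wording only, at the price of a less favourable figure; it corrects the claim but does not raise power.

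2. **Secondary: the infected set.** Show the formula and inputs behind 757, or restate power at a 10% base risk as about 77% for 757 positives and 84% for about 908. Say which prevalence the adopted total uses, and note that power is higher if the full composite has a base risk above 10% (89% at an assumed 15% with 757). Also wording only.

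3. **Before making positives the primary set,** reconcile Questionnaire and follow-up and the Annual Plan, which indicate urine at baseline, with the two sections that delay control urine. If enrolment urine exists for controls, define positivity at enrolment in both arms; that is wording only. If control status is known only after the outcome, label the comparison as open to bias, do not make it primary, and keep the all-randomised comparison with its low power stated. Under delayed collection, an enrolment-positive primary analysis would need urine collected, stored and later tested for about 7,725 controls. The laboratory section describes no storage up to delivery, and holding untested samples would need ethics review.

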We will adopt the block randomization approach. Specific randomization steps include: 1) After we recruit participants, we will group them into blocks on a chronological basis. Each block will have 20 women who will be numbered sequentially. 2) We will then randomly divide them in each block into intervention and control groups. That is numbering the participants from 1 to 20, then generating 10 random numbers and the corresponding participants will be assigned to the intervention group. For participants in the intervention group, we will immediately test for *C. trachomatis* and *Neisseria gonorrhoeae* (See Figure 1 for the flowchart of the study design). Participants who test positive for either infection in the intervention group will be linked to physicians at the Center for treatment. For the control group, urine samples will be collected and tested immediately after childbirth or in the event of an adverse pregnancy outcome. In the event of a positive test result, the participant will be suggested to return to the Center for further treatment.

[figure not shown]

Figure 1, Flow Chart of the study.

Intervention and Treatment

This RCT will follow the principle of nonmaleficence. For pregnant women enrolled in the intervention group, after completing the test, laboratory personnel will inform the researchers of positive results. The sample number of the positive result will then be reported to the Guangzhou Women and Children Medical Center (GWCMC). The center's physicians will match the result to the correct patient and notify them of their results. We will provide a training session to the physicians at the Center about the national standard treatment plan (Azithromycin 1g, single oral administration). They will be suggested to treat patients according to the Chinese clinical and

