prevention guidelines for sexually transmitted diseases, and final decision will be made by the physician and patient together. Physicians will ask patients to return to the women's center for test of cure and re-testing in one month and three months after treatment respectively. At each of these visits, we will collect urine samples for Chlamydia testing. Patients who still test positive will continue treatment until they test negative. Additionally, pregnant women who test positive for Chlamydia will also be suggested to bring Azithromycin home to treat their spouses. We will also caution them to avoid sexual activity during the treatment period (7-10 days starting from day of treatment). We will also provide consultation services for the participants to deal with intimate partner relationship under this circumstance.

For pregnant women enrolled in the control group, we will delay the urine sample collection and the test until after delivery, or in the event of adverse pregnancy outcomes. In the event of a positive test, the patients will be informed of the positive test results the same way as the intervention group. In the event of a positive test, physicians will be suggested to provide patients and their spouses with treatment identical to the intervention group. In the event of a negative test, there will be no need for treatment. Specific treatment options will be the same to the intervention group. Physicians will ask patients to return to the Center one month after treatment for test of cure. Endpoint of the study is defined as either the occurrence of an adverse pregnancy outcome or delivery of a newborn.

After delivery, all patients who tested positive will be informed of the risk of Chlamydia infection in neonates. About 1-week post-partum (including Caesarean newborns), neonatal conjunctival scrapings and nasopharyngeal/pharyngeal swabs will be collected. In addition, infants will be examined for neonatal conjunctivitis and / or pneumonia clinical symptoms (see details in secondary outcome). In the case of a confirmed diagnosis, treatment will be carried out.

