If there is no confirmed diagnosis, family of the newborn will be advised to pay close attention for the emergence of signs of conjunctivitis and / or pneumonia, and promptly return to the hospital if the post-neonatal clinical symptoms appear. This study will follow the treatment guidelines for of the American Academy of Pediatrics Infectious Diseases and America Centers for Disease Control and Prevention for conjunctivitis and pneumonia: Erythromycin 12.5 mg/kg, oral, 4 times a day, for 14 days. For patients that do not return to the hospital for screening, the research team will call patients and verify the newborn infection status and whether treatment was provided at a different hospital.

Justifications of the control strategy

Currently in China, there are no clinical guidelines or policies that suggest routine genital chlamydia screening in pregnant women.¹⁵ The clinical standards for conducting a chlamydia test in pregnant women include relevant symptoms including urethritis, cervicitis and occurrence of adverse pregnant outcomes.¹⁵ Compared to current standard care (i.e., no routine screening and treatment), both our intervention (free screening for chlamydia at recruitment and linkage to care) and control (free screening for chlamydia at delivery of the baby and linkage to care) strategies provide better care to the target group.

Safety management plan

Criteria for withdrawal: if participants want to quit the study for any reasons; occurrence of any adverse pregnancy outcomes or recommendation by their personal physician to stop participation; Data and safety monitoring will be done by The Center and the Dermatology Hospital of Southern Medical University.

In addition, the study complies with the following statements: Any risk is the least possible for achieving the objectives of the research; Each individual providing consent is fully informed regarding the reasonably foreseeable impact of the research on the fetus or neonate; No inducements, monetary or otherwise, will be offered to terminate a pregnancy; Individuals engaged in the research will have no part in any decisions as to the timing, method, or procedures used to terminate a pregnancy; and Individuals engaged in the research will have no part in determining the viability of a neonate.

Primary Outcome

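### Newborn pneumonia, a secondary outcome expected at 4-12 weeks, is examined at a stated infant age only at about 1 week, so cases are likely to be missed

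*Combined protocol and SAP*

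**What the plan says.** Section III, Hypothesis 2, expects screening and treatment to lower chlamydial conjunctivitis and pneumonia in newborns. Under Secondary Outcomes (section IV), newborn pneumonia is listed with newborn *C. trachomatis* infection and chlamydial conjunctivitis. Conjunctivitis is placed at 5-14 days after birth. For pneumonia, "symptoms will usually appear in 4-12 weeks"; onset is described as insidious and fever as uncommon.

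The infant assessment is described under Intervention and Treatment, for infants of women who tested positive: "About 1-week post-partum (including Caesarean newborns), neonatal conjunctival scrapings and nasopharyngeal/pharyngeal swabs will be collected". A clinical examination for conjunctivitis and pneumonia goes with it, and "In the case of a confirmed diagnosis, treatment will be carried out". If nothing is confirmed, families are told to watch for signs of either condition and to "promptly return to the hospital if the post-neonatal clinical symptoms appear". The team telephones those who do not come back for screening, to ask about the infant's infection status and any treatment at another hospital. No timing is given for that call.

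The same section says: "Endpoint of the study is defined as either the occurrence of an adverse pregnancy outcome or delivery of a newborn".

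Mothers are tested at different times by arm. Under Participant recruitment and randomization, "For participants in the intervention group, we will immediately test for" the two infections, whereas for controls "urine samples will be collected and tested immediately after childbirth or in the event of an adverse pregnancy outcome". Positive women in the intervention arm are asked back one and three months after treatment. Positive controls are asked back one month after treatment that follows delivery.

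**The concern.** The one examination with a stated infant age comes before the disease is expected to show itself. What follows is passive or has no date, and the plan itself describes an illness that families may not recognise or bring to hospital. A plan followed exactly as written could therefore record few pneumonia cases in either arm. A null result for that half of Hypothesis 2 could then reflect when infants were examined rather than what treatment did.

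If capture were equally incomplete in both arms, the expected risk ratio would be unchanged. The absolute risks would be too low, and the estimate would be less precise. If capture differed by arm, the comparison itself could be biased, and the plan gives some reason to ask. A positive control mother has a hospital visit near the time the pneumonia window opens. A positive intervention mother's visits are timed from treatment that follows testing at enrolment, and many may fall before birth.

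**Working it through.** **Timing.** The plan gives no figure to reproduce here, so the check is to list every contact that could record infant pneumonia and compare it with weeks 4-12.

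| Contact (section) | Stated infant age | Infant examined? |
|---|---|---|
| Swabs and clinical examination (Intervention and Treatment) | about 1 week | yes |
| Return if symptoms appear (same) | none; family-initiated | on return |
| Call to those not returning (same) | none | no; verbal report |
| Maternal visits after treatment (same) | none; timed from the mother's treatment | not stated |
| Neonatal symptom item (Clinical Data Collection) | none | not stated |
| Post-delivery survey line (VIII. Annual Plan) | none | not stated |
| Birth-cohort visits (VI. Research Foundation) | 6 weeks, 6 months and later | not made a trial contact |

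Gap from the dated examination to the opening of the window: 28 - 7 = 21 days. Gap to its close: 12 - 1 = 11 weeks. There is no overlap. For conjunctivitis (days 5-14), an examination at about day 7 comes before any onset on days 8-14.

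**Contact by arm.** Control women are tested after delivery and, if positive, treated and asked back a month later. Their infants would then be at least about four weeks old, near the start of the window. Intervention women are tested at enrolment, which may occur at any gestational age, and return one and three months after treatment. Many of those visits may precede birth. The documents give no distribution of gestational age at enrolment, so the share cannot be computed.

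**Scale.** Expected control-arm cases = positive women per arm x risk of pneumonia.

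Inputs:
- Risk of 5-15% by mother-to-child transmission, from the background.
- Positive women per arm, two versions from Sample size estimation: 757 / 2 = 378 (80% power row), and 0.06 x 7,725 = 463.5, about 464.

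Results:
- 378 x 0.05 = 18.9 and 378 x 0.15 = 56.7: about 19-57 cases.
- 464 x 0.05 = 23.2 and 464 x 0.15 = 69.6: about 23-70 cases.

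The two bases are not quite alike. The table's total is 757 / 0.05 / 0.98 = 15,449, so 378 is net of the 2% loss. The 464 is gross; net, it is 463.5 x 0.98 = 454. That hardly moves the range: 454 x 0.05 = 22.7 and 454 x 0.15 = 68.1, or about 23-68.

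**Calls for the remedy.** 757 (table); 0.06 x 15,450 = 927; 0.08 x 15,450 = 1,236.

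**The case against.** The plan does not ignore later disease. Its advice to families refers expressly to post-neonatal symptoms and names pneumonia. The call asks about treatment elsewhere, and pneumonia is on the neonatal data list. A reader might infer that there is no infant follow-up after week 1; the documents do not support that. Nor does the endpoint definition show that observation of infants stops at delivery, since the swabs themselves come later. The fair criticism is that later capture is passive and undated. It is also unclear whether the call follows a missed week-1 visit or a missed later return.

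Figure 1 and the annexes are not available here. The flow chart could carry contact timing, so the absence of a dated contact is established only for the available text. The word usually also leaves room for some cases at week 1.

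The birth cohort's 6-week visit falls inside the window. However, it is described as institutional background, no text assigns trial infants to it, and the cohort had not yet begun at Zengcheng.

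A reader might also infer that the control arm's later visit biases the result by a known amount. The documents do not support that. No infant examination is stated at any maternal visit, and the week-1 procedures are the same in both arms.

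Finally, under-ascertainment is an inference. The documents give no capture rate, so neither the number of missed cases nor the loss of power can be derived from them.

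**Conclusion.** The point stands as a weakness in how one secondary outcome is ascertained, and it should be corrected. In the text available, the only dated infant examination is about three weeks too early for the plan's own pneumonia window, and nothing later is tied to an infant age. Pneumonia is likely to be under-counted; conjunctivitis beginning on days 8-14 is affected to a lesser degree.

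About 19-57 or 23-70 control-arm cases are at issue, depending on the number of positive women. These figures assume that infection stays untreated until delivery, that each mother has one live infant, and that the background's 5-15% applies. They are not bounds: prevalence may be higher, and treating infants confirmed at week 1 may lower the count. Capture may differ by arm, but no size of bias is claimed.

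It would go too far to conclude that Hypothesis 2 as a whole, or the trial, is undermined. Newborn laboratory infection measured at week 1 is unaffected, and so is the primary outcome, which does not include pneumonia.

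**What to change.** 1. Extend the existing call to one scripted call at about 12 weeks of infant age, the same in both arms, to all chlamydia-positive mothers with a live infant. Record pneumonia and conjunctivitis diagnoses, dates, laboratory confirmation and treating hospital.
2. A call cannot establish a chlamydial cause. Where a diagnosis is reported, obtain the existing hospital records. Report laboratory-confirmed chlamydial pneumonia separately from all-cause pneumonia.
3. Describe the comparison as not strictly randomised. Infants are followed only if the mother tested positive, and intervention mothers are tested at enrolment while for controls "we will delay the urine sample collection and the test until after delivery, or in the event of adverse pregnancy outcomes". Counts over all women randomised are a useful supplement, but they do not remove this problem, because case-finding still depends on a positive test obtained at arm-specific times.
4. If Figure 1 or an annex already fixes a later infant contact, state its infant age and content in the Secondary Outcomes section.

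Cost: about 757 to 1,236 calls, record requests only where a diagnosis is reported, and reliance on parental report for the first step.
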